## Safety

- [1] Vital signs (body temperature, blood pressure systolic/diastolic, pulse rate)
- [2] Laboratory tests (routine blood tests, clinical chemistry tests, urine analysis, coagulation tests)
- [3] Immunogenicity (anti-drug antibodies, neutralising antibodies)
- [4] Adverse events other than CIPN

	Pharmacokinetics
	Blood concentration of thrombomodulin alfa (recombinant)
Treatment and	Screening period: up to 14 days
observation periods	Treatment period: 24 weeks (up to 36 weeks)
	Follow-up period: 4 weeks (up to 6 weeks)
Target sample size	75 subjects (25 per group)
Study period	July 2016 to January 2018
Primary analysis	[1] Analysis set
methods	The primary efficacy analysis set is the full analysis set (FAS).
	[2] Handling of primary efficacy data
	Handling of missing data on whether an assessment is NCI-CTCAE
	Grade 1 or greater
	Consider subjects for whom these data are missing to have had an
	NCI-CTCAE Grade 1 or greater event. Perform sensitivity analysis
	that includes analysis with a missing NCI-CTCAE grade for all such
	subjects.
	Handling of NCI-CTCAE evaluation data in the second and
	subsequent courses
	Evaluate the Day 1 (baseline) NCI-CTCAE grades as those from
	the immediately preceding course. Evaluate the Days 2, 3, 15, and 29
	NCI-CTCAE grades as those observed within the course.
	Handling of missing efficacy endpoint data (continuous variables)
	Do not impute missing continuous efficacy endpoint data. Perform
	sensitivity analyses with imputation using the
	last-observation-carried-forward (LOCF) approach.
	[3] General matters pertaining to efficacy analysis
	This study is conducted to assess and characterize the clinical effect of
	ART-123 for preventing the onset of oxaliplatin-induced peripheral
	neuropathy and to explore appropriate efficacy indices. Thus, efficacy
	analyses will be performed primarily with descriptive statistics obtained
	by summarizing and graphing data from each evaluation time point.
	The incidences of NCI-CTCAE Grade 1 or greater events will be
	evaluated with statistical tests and 95% confidence intervals as necessary
	in addition to descriptive statistics to allow intergroup comparison. The
	incidences of NCI-CTCAE Grade 1 or greater events with
	discontinuations and dropouts factored in will also be estimated.
	The significance level is set at 5% (two-sided), with a two-sided
	confidence interval and a confidence coefficient of 95%. Given the

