#### 9.7.4 Adverse Events

#### 9.7.4.1 Definition of Adverse Events

An adverse event is defined as any untoward or unintended disease or sign (including abnormal laboratory findings and vital signs) that occurs after informed consent. Any adverse event occurring after investigational product administration is considered a treatment-emergent adverse event (TEAE). When a diagnosis can appropriately be assigned for an adverse event, that diagnosis rather than the symptom or sign will be the adverse event name. Abnormal laboratory findings and vital signs are constituted when:

- [1] An abnormal laboratory finding or vital sign satisfies the definition of a serious adverse event.
- [2] An abnormal laboratory finding or vital sign results in the suspension or discontinuation of the investigational product.
- [3] An abnormal laboratory finding or vital sign results in the use of a drug or intervention for treatment.
- [4] The physician determines that an abnormal laboratory finding or vital sign is of a medically significant severity (e.g., is an abnormality consistent with [2] or [3] above but there was no opportunity for intervention).

CIPN will not be considered an adverse event in this study.

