# 9.7.4.4 Assessing Adverse Events

#### 9.7.4.4.1 Seriousness Classifications

The investigator or subinvestigator will classify each adverse event as a serious adverse event or non-serious adverse event according to the criteria given below. For serious adverse events, the reason will be selected from items 1 to 6 below.

- > Serious adverse events:
  - 1: Results in death (death)
  - 2: Life threatening (possibility of death)
  - 3: Requires hospitalization or prolongation of hospitalization for treatment (hospitalization or prolongation of hospitalization)
  - 4: Persistent or significant disability or incapacity (disability)
  - 5: Is a congenital anomaly (congenital anomaly)
  - 6: Other medically significant condition (possibility of disability, seriousness consistent with 1 to 4 above)
- Non-serious adverse events:

This refers to all adverse events that are not serious adverse events.

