# 10.3 Actions to Take for Serious Adverse Events

# 10.3.1 Procedures for Investigator or Subinvestigator

When a serious adverse event occurs, the investigator or subinvestigator will promptly notify the sponsor and study site director orally or by telephone, fax, or a similar means regardless of the causal relationship to the investigational product. The sponsor will be notified no later than 24 hours after a serious adverse event is identified.

The investigator will complete a written report about each serious adverse event (using the specified form of the study site or sponsor) for submission to the sponsor and study site director. With the first reporting day as Day 0, the investigator will submit the written report to the sponsor by Day 4 if the event is a death or life threatening or by Day 7 if the event is another serious adverse event.

The investigator or subinvestigator will comply with any instructions of the study site director based on the findings of the institutional review board about whether the study should continue and the instructions of the sponsor about amending the protocol or taking other appropriate actions.

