# > Full analysis set (FAS)

This population consists of all subjects assigned to the investigational product except:

- Subjects with a GCP violation
- Subjects who do not receive oxaliplatin
- Subjects who do not receive the investigational product
- Subjects with no available efficacy data following investigational product administration

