#### 12.7 Safety Analysis

#### 12.7.1 Analysis of Adverse Events

TEAEs evaluated in the study will conform to the definition in Section 9.7.4.1. All TEAEs identified from the first day of investigational product administration to study completion (Day 43 of the last course) will be included in the tabulations. The numbers of subjects with a TEAE in each treatment group will be tabulated by adverse event name, organ class, severity (per NCI-CTCAE grading), seriousness classification, causality, and the timing of onset. Differences from the placebo group in TEAE incidences will be calculated along with two-sided 95% confidence intervals of these differences.

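### CIPN is excluded from adverse events without exception, so neuropathy that meets a seriousness criterion gets no expedited report, no causality assessment and no adverse event follow-up

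*Protocol*

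**What the plan says.** The definition of adverse events in section 9.7.4.1 ends with a flat exclusion: "CIPN will not be considered an adverse event in this study". The Synopsis and section 5.1 carry the same decision into the safety endpoints, where the fourth item reads "Adverse events other than CIPN".

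The safety procedures that follow are all written for adverse events. Section 9.7.4.4.1 opens with "The investigator or subinvestigator will classify each adverse event as a serious adverse event or non-serious adverse event according to the criteria given below", and its list includes hospitalisation, lasting disability and other medically significant conditions. Section 10.3.1 sets the deadline: "The sponsor will be notified no later than 24 hours after a serious adverse event is identified". Written reports follow by Day 4 or Day 7, and section 10.3.2 then has the sponsor consider whether the study should go on. For the tables, section 12.7.1 says "TEAEs evaluated in the study will conform to the definition in Section 9.7.4.1".

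CIPN is collected as efficacy instead. Section 9.6.3.1 grades motor and sensory neuropathy from none to Grade 5, and section 12.6.2.1 tabulates the grades by time point and group.

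**The concern.** Keeping the endpoint event out of the routine adverse event listing is a normal choice in a prevention trial. It avoids double counting and a flood of forms for an effect expected in most subjects. That reason covers ordinary CIPN. It does not extend to a case that hospitalises or disables a subject, which is the kind of case that expedited reporting exists to bring to the sponsor within a day.

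Section 3.3.1 describes this as the first study of the drug's efficacy in CIPN, so the direction of its effect on nerves is not established. If a subject has unusually severe neuropathy, nobody is asked to judge whether the investigational product contributed, and the sponsor has no dated obligation to look at the case.

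**Working it through.** No figure in the protocol bears on this point, so the check is a trace through the text.

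**Step 1. Does CIPN reach each safety procedure?**

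| Procedure | Section | Starts from | CIPN included? |
|---|---|---|---|
| Recording of outcome, seriousness and causality | 9.7.4.2 | adverse event | no |
| Seriousness classification | 9.7.4.4.1 | adverse event | no |
| Causal relationship to the investigational product | 9.7.4.4.3 | adverse event | no |
| 24-hour notice, Day 4 or Day 7 written report | 10.3.1 | serious adverse event | no |
| Sponsor's review | 10.3.2 | written serious event report | no |
| Follow-up to resolution or stabilisation | 9.7.4.5, 11.5 | adverse event | no |
| TEAE tables | 12.7.1 | TEAE as defined in 9.7.4.1 | no |

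Each row depends on the definition in 9.7.4.1, and no other section brings serious CIPN back in.

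**Step 2. Could CIPN meet a seriousness criterion?** Yes, on the protocol's own account. Section 1.1.3 lists difficulty walking among the chronic manifestations, says risk rises with cumulative oxaliplatin dose, and says symptoms may last for months or years. That can fit the disability criterion in 9.7.4.4.1.

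**Step 3. Does the protocol make such an exception elsewhere?** Twice. In 9.7.4.1, an abnormal laboratory value or vital sign counts as an adverse event once it meets the definition of a serious one. In 10.4, pregnancy is generally not an adverse event, yet specified outcomes are treated as serious adverse events. CIPN has no equivalent clause.

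**Step 4. Does efficacy capture fill the gap?** Sections 9.6.3.1, 12.6.2.1, 12.6.2.2 and 12.6.2.6 cover grades, DEB-NTC symptoms and oxaliplatin changes due to CIPN. None records seriousness, causality or outcome. Grade is a severity scale and does not replace the seriousness judgement.

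On timing, section 15.1 requires eCRF entry to be completed promptly after follow-up or discontinuation, and leaves other entry timing to a data entry handbook. For a subject who completes the study, treatment may last 36 weeks and follow-up 6 weeks (Synopsis, 5.3). The only completion point that the protocol itself fixes may therefore fall 36 + 6 = 42 weeks after the first dose, against 24 hours for a serious adverse event. The handbook may require earlier entry.

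**Step 5. How long is CIPN observed?** Scheduled assessment ends at study completion, on Day 43 of the last course with a 14-day window. Follow-up under 9.7.4.5 continues until an adverse event resolves or stabilises. CIPN persisting at study completion is outside that requirement.

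**The case against.** The exclusion is deliberate and consistent. It appears in the Synopsis, 5.1 and 9.7.4.1, and CIPN is a separate reason code from adverse event in 9.4 and 11.1. Other routes can also bring a bad case to the sponsor's notice:

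- Progression of the targeted disease is a reason for discontinuation (11.2.1), and the sponsor must be told promptly of every discontinuation (11.4.2).
- Emergency unblinding covers occurrences comparable to a serious adverse event (6.7).
- Termination or suspension can follow an incident similar to a serious adverse reaction (14.3).

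These routes are real, but none is a timed report of a serious CIPN case with a causality judgement, and a subject with serious CIPN who stays in the study need not trigger any of them.

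The boundary is also imprecise. Table 9.7-1 places disability at Grade 3, and 1.1.3 expects long-lasting symptoms, so the disability criterion may be met more often than intended. That stands as a caution on cost.

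Three stronger readings are tempting, and the documents support none of them:

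- **A reader might infer that worsening caused by the drug would go unseen.** It would not. CIPN is graded on Days 1 to 3 of each course, on Day 15 of course 12, at completion and at discontinuation. Section 12.6.2.1 plans incidence by group, differences from placebo and Kaplan-Meier curves.
- **A reader might infer that dosed subjects outside the FAS have their CIPN tabulated nowhere.** The exclusion "Subjects with no available efficacy data following investigational product administration" removes subjects who have no post-dose CIPN grade to tabulate, and subjects without oxaliplatin cannot have the neuropathy under study. Only dosed subjects excluded for a GCP violation remain.
- **A reader might blame the lack of an interim analysis.** Sections 5.1 and 12.9 leave every kind of event without group-level review before unblinding, and reporting serious CIPN would not supply it.

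**Conclusion.** The point holds as a gap in safety reporting. CIPN that meets a seriousness criterion is never classified for seriousness or causality. It does not trigger the 24-hour or written reports or the sponsor's serious event review, and it is outside adverse event follow-up. Graded CIPN remains in the efficacy tables, so the loss is confined to those items.

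The size cannot be given as a number of cases. The protocol states no rate of serious CIPN, and any count would only restate an assumed share of the 75 planned subjects. The conclusion does not need one, since it rests on the wording of the sections traced above. It assumes that no sponsor procedure outside the protocol already requires serious CIPN to be reported. It concerns chemotherapy-induced neuropathy only, because neuropathy attributed to another cause remains an adverse event. This is a cheap improvement to safety reporting.

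**What to change.** 1. In 9.7.4.1, replace the flat exclusion with a conditional one: *CIPN is not treated as an adverse event unless it meets a seriousness criterion in 9.7.4.4.1, in which case it is reported under 10.3.1.* Causality, sponsor review and follow-up then apply through the existing sections.
2. In the Synopsis and 5.1, change the fourth safety endpoint to *Adverse events other than non-serious CIPN*. Without this, both places would contradict the amended definition.
3. In 12.7.1, state that serious CIPN is tabulated by group in the safety population, in its own table and separate from the main TEAE tables. Because 12.7.1 takes its definition from 9.7.4.1, serious CIPN would otherwise enter the main tables automatically.

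The cost is some additional serious adverse event forms, whose number is unknown for the reason given under the objection, and one table. The eCRF instructions should also say how to code a discontinuation for serious CIPN, which could otherwise fall under either adverse event or lack of efficacy in 11.2.1. Nothing changes in dosing, visits or the efficacy analysis.

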# 9.7.4.2 Identification of Adverse Events

The investigator or subinvestigator will identify adverse events spontaneously reported by the subjects and through interview and tests on each observation day.

Information to be determined:

Name of adverse event, date of occurrence, status of investigational product administration (discontinuation/suspension/no change [including completion]), date of outcome, outcome, seriousness classification, rationale for seriousness, severity, causal relationship to the investigational product, whether the subject was discontinued from the study

# 9.7.4.3 Adverse Event Reporting Period

Adverse events occurring from after informed consent to study completion (Day 43 of the last course) will be reported.

# 9.7.4.4 Assessing Adverse Events

#### 9.7.4.4.1 Seriousness Classifications

The investigator or subinvestigator will classify each adverse event as a serious adverse event or non-serious adverse event according to the criteria given below. For serious adverse events, the reason will be selected from items 1 to 6 below.

- > Serious adverse events:
  - 1: Results in death (death)
  - 2: Life threatening (possibility of death)
  - 3: Requires hospitalization or prolongation of hospitalization for treatment (hospitalization or prolongation of hospitalization)
  - 4: Persistent or significant disability or incapacity (disability)
  - 5: Is a congenital anomaly (congenital anomaly)
  - 6: Other medically significant condition (possibility of disability, seriousness consistent with 1 to 4 above)
- Non-serious adverse events:

This refers to all adverse events that are not serious adverse events.

# 9.7.4.4.2 Severity

The investigator or subinvestigator will assess the severity of each adverse event as Grade 1 to 5 based on NCI-CTCAE. The severity of adverse events not corresponding to the events in the glossary will be assessed according to the following criteria:

Table 9.7-1 Adverse event severity assessment criteria

Grade 1	Mild
	Asymptomatic or mildly symptomatic
	Clinical findings or laboratory test findings only
	Treatment not indicated
Grade 2	Moderate
	Minimal/local/non-invasive treatment indicated
	Limiting age-appropriate instrumental activities of daily living a)
Grade 3	Severe or medically significant but not immediately life-threatening
	Hospitalization or prolongation of hospitalization indicated
	Disability/disabling
	Limiting self-care activities of daily living b)
Grade 4	Life-threatening consequences
	Urgent intervention indicated
Grade 5	Death related to an adverse event

a) Instrumental activities of daily living refer to preparing meals, shopping for groceries or clothes, using the telephone, managing money, etc.

b) Self-care activities of daily living refer to bathing, dressing and undressing, eating, using the toilet, taking medications, and being not bedridden.

Source: JCOG Japanese translation of the NCI Common Terminology Criteria for Adverse Events Version 4.0

# 9.7.4.4.3 Causal Relationships to Investigational Product

The investigator or subinvestigator will assess adverse event causality according to the criteria below. Events classified as item 1 will be handled as adverse reactions.

#### 1. Related

When there is a reasonable possibility that the investigational product caused the adverse event. The causality will be assessed as "related" when a reasonable possibility that the investigational product caused the adverse event is not evaluable.

#### 2. Not related

When there is no reasonable possibility that the investigational product caused the adverse

# 9.7.4.5 Follow-up for Adverse Events

All adverse events will be followed until resolution or return to baseline level or until the symptoms/test values are found to have stabilized and are no longer clinically significant. Data obtained during the period specified in Section 9.7.4.3 . will be entered in the eCRFs.

#### 9.8 Other Investigations/Observations and Evaluation Methods

#### 9.8.1 Pharmacokinetics (blood concentration of thrombomodulin alfa (recombinant))

The investigator or subinvestigator will collect samples from the subjects at the time points listed below, separate the plasma, and temporarily store the plasma before submitting the samples to the plasma concentration laboratory. Samples will be collected, processed, stored, and shipped as directed in written procedures to be submitted by the sponsor to each study site. The plasma concentration laboratory will determine plasma drug concentrations and submit the results to the sponsor after unblinding. As the sponsor will be electronically notified of the results, the data need not be input into the eCRFs. Only the times and dates of blood sampling should be entered.

# > Assessment time points

- Day 1 of course 1: Before investigational product administration and just after and 30 to 120 minutes after completion of investigational product administration
- Days 2 and 3 of course 1\*1: Just after and 30 to 120 minutes after completion of investigational product administration
  - \*1 To be performed once in any of courses 2 to 12 if blood is not sampled in course 1
- ➤ Blood sample volume: 3 mL
- > Information to be determined
  - Time and date of blood sampling

#### 9.8.2 Urine Pregnancy Testing

The investigator or subinvestigator will collect urine samples from subjects at the time points listed below and test for pregnancy in reference to human chorionic gonadotropin test (urine) findings. Only female subjects will undergo pregnancy testing. Testing is not required for women who have been postmenopausal for at least 2 years at informed consent. Male subjects will be interviewed at these testing times to determine if their partner is pregnant. Data will be entered in the eCRF only if the subject is female.

- Measurement time points: Screening period, Day 1 of course 2\*1, study completion
- > Information to be determined: Date of urine sampling, pregnancy status
  - \*2 May be determined on the day before Day 1

# 9.8.3 Pathology of CIPN and Exploratory Assessments of Efficacy and Safety of the Investigational Product

Collected serum and plasma samples that remain after immunogenicity and pharmacokinetic evaluations will be stored for up to 5 years after study completion in the immunogenicity assay laboratory and plasma concentration laboratory according to separately established sample handling procedures and may be used during this period to elucidate the mechanism of CIPN onset or the mechanism of action of Recomodulin or for research to develop drugs to prevent or treat CIPN. No genetic information will be handled. Any such investigations will be initiated in accordance with procedures established by the sponsor.

# 10. Ensuring Subject Safety

#### 10.1 Basic Information

The investigator or subinvestigator will determine patient eligibility by conducting observations and examinations at the time of screening and will not enroll a patient in the study when safety cannot be ensured.

The investigator or subinvestigator will investigate the health of the subjects on each observation day during the study and ensure that emergency contact is possible. If a subject-reported or other adverse event occurs, the investigator or subinvestigator will promptly take appropriate actions as necessary for ensuring subject safety.

The sponsor will appropriately collect and relay any safety information relevant to the study.

The investigator or subinvestigator will endeavor to identify adverse reactions early by closely monitoring subject symptoms.

# 10.2 Particularly Notable Information

# 10.2.1 Precautions Related to Bleeding

Because Recomodulin has anticoagulant activity and could potentially cause or exacerbate bleeding symptoms, the drug must be administered with bleeding symptoms sufficiently managed. If a bleeding-related serious adverse event occurs, Recomodulin administration will be discontinued as necessary, and appropriate intervention, such as transfusion, will be provided as necessary.

#### 10.2.2 Interventions for Overdoses

There is no drug that is known to neutralise the anticoagulant activity of Recomodulin. In the event of an accidental overdose, discontinue administration of Recomodulin and give intravenous fluids, a transfusion, or other intervention to reduce plasma levels as necessary while closely monitoring for worsening of bleeding tendencies and changes in coagulation activity and the like.

